**Table 1. Schedule of Assessments: Part 1**

Visit Identifier	Screening	Treatment Period Cycle 1					Treatment Period (each 28 Day Cycle)		EOT Visit	FU Visit	LTFU	Notes/Protocol Section
		Day1	Day4	Day8	Day15	Day22	Cycles 2-6 Day1	Cycle7 Onwards Day1				
Visit Window	Day-28 to Day-1	-	-1/+3 D	-1/+3 D	±3D	±3D	±3D	±3D	14 D post- final dose	28 to 35 days post- final dose	±14D	
Imaging (PET/CT, CT or MRI)	X	Time points for disease assessments described in notes									At screening, as clinically indicated if EMD is suspected, and annually. For participants with measurable EMD (paramedullary disease or plasmacytomas associated with bone are not considered EMD) at screening, every 12 wks (±1 wk) and at suspected CR/sCR. Participants with non-measurable EMD must be assessed at suspected CR/sCR. Once all EMD has resolved/disappeared, imaging can be conducted annually (or earlier if clinically indicated) and at suspected PD. For participants with only skin involvement, skin lesions should be measured with a ruler every 4 wks (+ 1 wk). Perfolm until PD, withdrawal of consent, participant lost to follow-up, death, or defined end of study. See Section 8.1.3.	

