### **8.1. Efficacy Assessments**

All disease responses will be assessed according to IMWG response criteria ([Appendix 10](#)) and entered on the CRF. All response categories (except stable disease) require 2 consecutive assessments (confirmation).

Disease assessments are to be conducted per [SoA](#) 28-day ( $\pm 1$  wk) interval whether dose given or not (ie, the 28-day interval [ $\pm 1$  wk] from C1D1 should be maintained regardless of dose delays/interruptions).

Disease assessments should continue until confirmed PD, withdrawal of consent, lost to follow-up, death, or defined end of study (whichever occurs first).

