- Involved and uninvolved serum FLC analysis, are required at screening, C1D1 and when both serum and urine M-components are deemed non-measurable (including at suspected CR). Serum free kappa, free lambda and free kappa/lambda ratio will be collected. Participants with measurable disease by SPEP or UPEP cannot have response assessed by serum FLC. Except for sCR, serum FLC levels should only be used for response assessment when both the serum and urine M component levels are deemed not measurable or uninterpretable. Serum FLC cannot replace UPEP/UIFE in any situation where urine M component is measurable at baseline.
- **Note:** For participants treated with daratumumab, isatuximab and elotuzumab less than 114 days prior to C1D1, daratumumab, isatuximab and elotuzumab may interfere with SPEP, and SIFE. Therefore, for these participants, serum FLC assay should be completed at screening, C1D1, and along with all subsequent disease assessments. Serum M-protein (M-spike), if measurable at baseline, should also be followed at the same time points as serum FLC with the most representative marker of disease status used for IMWG assessment.

On days of elranatamab administration, all samples will be collected prior to dosing.

In participants with 2 M-protein bands at baseline, unless the second band is due to daratumumab or other therapeutic mAb interference, the sum of the 2 spikes should be used for monitoring of disease.

PD must be confirmed (unless due to EMD). When PD (clinical or biochemical) is suspected, applicable tests (eg, SPEP, SIFE, UPEP, UIFE, serum FLC tests) should be repeated for confirmation prior to initiation of new anticancer therapy. To confirm PD, 2 discrete samples are required, and testing cannot be based upon the splitting of a single sample.

Note that if a participant had measurable serum or urine M-protein (M-spike) at baseline, unless the band is due to/confounded by the presence of daratumumab or other therapeutic mAb, PD cannot be defined by increases in serum FLC alone. Serum FLC levels should only be used for response assessment when both the serum and urine M-component levels are deemed not measurable or uninterpretable. Furthermore, careful attention should be given to new positive immunofixation results appearing in participants who have achieved a CR,

PFIZER CONFIDENTIAL

CT02-GSOP Oncology Clinical Protocol Template (01 March 2021)

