### 8.1.3. Imaging Assessments (PET/CT, CT and/or MRI)

Imaging will be completed for evaluation of disease response according to IMWG criteria at the time points specified in the [SoA](#). For participants with only skin involvement, skin lesions should be measured with a ruler at time points specified in the [SoA](#).

Screening images will be used to determine evaluable lesions for each participant. The same imaging technique should be used throughout the study (pre- and post-baseline assessments).

Bone lesions and any soft tissue plasmacytoma documented at baseline must undergo serial monitoring. Paramedullary disease or plasmacytomas associated with bone are not considered EMD. Plasmacytoma measurements should be taken from the CT portion of the PET/CT, or MRI scans, or dedicated CT scans where applicable. Any plasmacytoma that has been irradiated will not be suitable for response assessment; however, it must be monitored for PD.

Measurement of lesion size will be determined by the SPD.

Radiologic progression observed within the first month following the first dose of elranatamab will not be considered progressive disease.

Imaging obtained per the participant's standard of care prior to study enrollment and signing of consent do not need to be repeated and are acceptable to be used as baseline evaluation, if, (1) obtained within 42 days before start of study intervention, (2) the same technique can be used to follow identified lesions throughout the study for a given participant, and (3) appropriate documentation is available in the participant's source notes indicating that these assessments were performed as standard of care.

All participant's files and radiologic images must be available for source verification.

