**Table 16. Modified IMWG Response Criteria**

Response*	Modified IMWG Criteria
	at baseline, a 50% reduction in the size (SPD) of soft tissue plasmacytomas is also required. d
No Change/Stable Disease (SD)	
 
• Not meeting criteria for sCR, CR, VGPR, PR, MR or PD.
 

Progressive Disease (PD) b,c,f	
Any one or more of the following criteria:
 
 
• Increase of <math>\geq 25\%</math> from lowest confirmed response value in any 1 or more of the following:e,f 
 
Serum M-component (the absolute increase must be <math>\geq 0.5</math> g/d.L);
 
Serum M-protein increase <math>\geq 1</math> g/d.L, if the lowest M component was <math>\geq 5</math> g/d.L;
 
Urine M-protein (the absolute increase must be <math>\geq 200</math> mg/24 h).
 
 
 
In participants without measurable serum and urine M-protein levels, the difference between involved and uninvolved serum FLC levels (absolute increase must be <math>> 10</math> mg/d.L);
 
In patients without measurable serum and urine M-protein levels and without measurable involved serum FLC levels, CCI 
 
- <math>\geq</math> percentage irrespective of baseline status (absolute increase must be <math>\geq 0\%</math>)
 
 
 
• Appearance of a new lesion(s), <math>\geq 50\%</math> increase from nadir in SPD of <math>> 1</math> lesion, or <math>\geq 50\%</math> increase in the longest diameter of a previous lesion <math>> 1</math> cm in short axis.d
 
• <math>\geq 50\%</math> increase in circulating plasma cells (minimum of 200 cells per <math>\mu</math>L) if this is the only measure of disease
 

a All response categories require 2 consecutive assessments made any time before starting new therapy. Each category (except stable disease) will be considered unconfirmed until confirmatory test is performed. All categories (stable disease or better) require no known evidence of PD, new bone lesions or EM plasmacytomas if imaging studies were performed; imaging studies are not required to satisfy these response requirements except for requirement of FDG PET to confirm imaging plus MRD-negative.

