**CCI**

c Presence/absence of clonal cells is based upon the  $KL/\lambda$  ratio. An abnormal  $KL/\lambda$  ratio by IHC or immunofluorescence requires a minimum of 100 plasma cells for analysis. An abnormal ratio reflecting presence of an abnormal clone is  $KL/\lambda$  of  $> 4:1$  or  $< 1:2$ .

d Plasmacytoma measurements should be taken from the CT portion of the PET/CT, or dedicated CT scans where applicable. Measurement of tumor size will be determined by the SPD.

e PD confirmation requires 2 consecutive assessments made at any time prior to the institution of any new anticancer therapy. If alternate therapy is started before confirming PD, any additional testing during subsequent therapy can be used to confirm PD. Participants will be considered to have PD if they meet the criteria for progression by a variable that was not considered measurable at baseline; however, for

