21	SD	sCR/CR/VGPR/PR/MR /SD/PD ^c	No further assessments	
22	sCR/CR/VGPR/PR/MR	NE/PD ^c or no further assessment	No further assessments	
23	PD ^c	sCR/CR/VGPR/PR/MR /SD	No further assessments	
24	PD ^c	PD (any reason) including PD after initiation of new anticancer therapy		PD
25	PD ^c	Participant died due to disease before further disease assessment (including death due to disease under study after initiation of new anticancer therapy)		
26	PD ^b	sCR/CR/VGPR/PR/MR /SD/NE/PD or no further assessments	No further assessments	
27	Death (due to disease under study) before initiation of new anticancer therapy			
28	Death (not due to disease under study)			NE
29	NE	No further assessment		
30	NE	NE/PD ^c	No further assessments	
31	PD ^c	NE	No further assessments	

EMD = extramedullary disease; IMWG = International Myeloma Working Group, sCR = stringent complete response, CR = complete response, PR = partial response, VGPR = very good partial response, SD = stable disease, PD = progressive disease, NE = not evaluable.
 
a. SD does not need to be confirmed.
 
b. PD due to EMD (includes any new lesion, increased extramedullary or paramedullary lesions, plasmacytomas), or bone marrow plasma cells does not need to be confirmed.
 
c. PD due to reasons other than EMD, or bone marrow plasma cells.
				

BOR by investigator will also be assessed programmatically based on derived responses per IMWG from the date of first dose until confirmed disease progression using IMWG response criteria, death or start of new anticancer therapy, whichever occurs first. This sensitivity analysis will follow the same rules as the secondary analysis except for deriving response based on the local laboratory and bone marrow data and the individual lesion data provided by the investigator.

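### SAP Table 4 note b counts paramedullary and bone-associated progression without confirmation, while the protocol places these lesions outside EMD, the only exemption it states

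*SAP*

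**What the plan says.** **Protocol.** Section 8.1.1 states "PD must be confirmed (unless due to EMD". Section 8.1.3 limits what EMD means: "Paramedullary disease or plasmacytomas associated with bone are not considered EMD". The imaging rows of the Part 1 and Part 2 schedules carry the same exclusion (in Part 1, "paramedullary disease or plasmacytomas associated with bone are not considered EMD"). The general rule in 8.1 is "All response categories (except stable disease) require 2 consecutive assessments (confirmation". Appendix 10, Table 16 repeats it in note a, "Each category (except stable disease) will be considered unconfirmed until confirmatory test is performed", and in note e, "PD confirmation requires 2 consecutive assessments made at any time prior to the institution of any new anticancer therapy". In their visible text, 8.1 and these two notes make no exception, not even for EMD.

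**SAP.** Table 4 in 6.3.1 splits progression into two classes. Note b describes PD due to EMD as including any new lesion and goes on: "increased extramedullary or paramedullary lesions, plasmacytomas), or bone marrow plasma cells does not need to be confirmed". Note c covers the rest, which must be confirmed: "PD due to reasons other than EMD, or bone marrow plasma cells". Section 6.3.1 applies these rules to PD as best response and to PD after a response, and dates PD at the first PD assessment. Sections 6.3.3 (DOR), 6.3.4 (DOCR), 6.3.5 (PFS) and 6.3.8 (MRD) all point back to Table 4.

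**The concern.** PFS, DOR and DOCR are defined in both documents through confirmed PD. Sites work to the protocol, so a growing paramedullary lesion is unconfirmed until a second assessment supports it. The programmer works to SAP Table 4, where the same lesion is PD on a single assessment. One participant's data can therefore give two different outcomes depending on which document is followed.

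No planned analysis would reveal this. The BOR sensitivity analysis in SAP 6.3.1 changes the source of the responses but keeps the same rules. The PFS and DOR sensitivity analyses in 6.3.5 and 6.3.3 deal only with COVID-19 deaths.

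**Working it through.** The plan gives no figure for this point, so the check is to compare the rules and trace identical data through both.

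**Step 1. Which types of progression are exempt from confirmation?**

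| Type of PD | Protocol | SAP Table 4 |
|---|---|---|
| EMD as the protocol defines it | Exempt in 8.1.1; no exemption visible in 8.1 or Table 16 notes a and e | Exempt (note b) |
| Paramedullary disease | Not EMD (8.1.3, both schedules), so needs confirmation | Placed inside EMD, exempt |
| Bone-associated plasmacytoma | Not EMD, so needs confirmation | Plasmacytomas listed without qualification, exempt |
| New lesion of any kind | Exempt only if it is EMD | Exempt |
| Serum or urine M-protein | Needs confirmation | Needs confirmation (note c) |
| Marrow plasma cells | No exemption visible, but 8.1.2 and a Table 16 note are redacted | Exempt |

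Rows 2 to 4 are the firm mismatch. Row 6 is left open.

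**Step 2. Trace the same assessments through Table 4.** Take a paramedullary PD. The SAP treats it as the note b type. Under protocol 8.1.1 and 8.1.3 it would be the note c type.

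| Assessments | SAP rule (note b) | Protocol rule (as note c) |
|---|---|---|
| PD, then SD, then none | BOR = PD (row 26) | BOR = SD (row 23) |
| PD, then NE, then none | BOR = PD (row 26) | BOR = NE (row 31) |
| PD, then CR, then CR | Response window closes at the first PD | BOR = CR (row 7) |
| PD, then PD | PD at the first date | PD at the first date (row 24) |
| PD, then death from the disease before reassessment | PD | PD (row 25) |

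The third line is how ORR and CRR can change. It assumes that PD needing no confirmation ends the BOR window in 6.3.1. The last two lines show that the rules agree once PD is confirmed.

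**Step 3. Time-to-event endpoints.** In the first two sequences the SAP rule gives a PFS event at the first PD date. The protocol rule gives no PD event, so the participant is censored unless a death supplies an event later. DOR and DOCR behave in the same way when such a PD follows a response. The MRD window closes at that PD under the SAP and stays open under the protocol rule.

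**Step 4. Scale.** The documents do not say how often such PD occurs or stays unconfirmed, so no expected number of events can be derived. For a proportion such as ORR, moving one participant is worth:
- planned RP2D group (8 from Part 2A plus 22 from Part 2B): 1/30 = 3.3 percentage points;
- RP2D group using the 11 participants that protocol 4.1 reports at Dose level 2, plus the planned 22: 1/33 = 3.0 points;
- all participants: 1/76 = 1.3 points.

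**The case against.** The best defence is that the SAP is allowed to differ. Protocol section 9 and SAP section 2 let it modify the protocol's analysis plans and require a matching amendment only for major changes to the primary endpoint. The endpoints here are secondary and descriptive, and the SAP applies one rule to all of them. That is correct, but a permitted departure still has to be visible. The SAP does not identify this one as a departure or give a reason. Its change table says only that the BOR rules were updated.

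Second, confirmation is not hard to obtain. Table 16 note e accepts testing during later therapy, and Table 4 rows 24 and 25 accept PD after new therapy and death from the disease. This stands, and it narrows the point to PD that is never confirmed by any of these routes.

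Third, version lag. The SAP, dated 15 July 2022, follows Amendment 2, and the amendment history dates the 8.1.3 sentence on paramedullary disease to Amendment 3. This may explain part of the mismatch. It may not explain all of it, because Amendment 2 is itself recorded as clarifying the EMD definition. Either way, the two supplied documents do not agree.

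Fourth, a reader might infer that waiving confirmation for marrow plasma cells also contradicts the protocol. The documents do not support that. Section 8.1.2, part of the PD row of Table 16 and a Table 16 note are redacted, and the missing note appears to be note b, which is attached to the marrow items and to PD. A marrow rule could sit there.

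**Conclusion.** The contradiction holds for paramedullary disease, bone-associated plasmacytomas and new lesions that are not EMD as the protocol defines it. For PD of these types that is never confirmed, the SAP records a PD event and the protocol rule does not.

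Two stronger readings go too far. One is that the documents count different PFS, DOR and BOR events in general: wherever PD is confirmed, both give the same event on the same date. The other is that a material share of PFS events is at stake. That would need the number of PDs, the share of these types and the share never confirmed, as well as deaths in the denominator, and the documents supply none of these. Nor does note b alone bring unconfirmed PD into these endpoints, since protocol 8.1.1 already exempts EMD.

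The size is therefore stated per participant: 3.3 percentage points in the planned RP2D group of 30. The Grade ≥2 CRS endpoint and its decision rule are untouched. The conclusion rests on the visible protocol text and on reading the unqualified mention of plasmacytomas in note b as including bone-associated ones.

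**What to change.** Before the final analysis, reconcile SAP Table 4 note b with protocol 8.1, 8.1.1, 8.1.3 and Table 16 notes a and e, so that both documents carry one EMD definition and one list of PD types exempt from confirmation. Editing note b alone is not enough, because 8.1 and the two table notes do not show even the EMD exemption. There are two ways to do it:

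- limit note b to EMD as the protocol defines it; or
- if the wider waiver is intended, declare it as a deliberate change in both documents and add a sensitivity analysis of BOR, PFS and DOR under the protocol rule.

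Under either option, apply the same rule to DOCR and the MRD window, and check the marrow waiver against the unredacted protocol. State also what counts as confirmation for a lesion seen only on imaging: the instructions in 8.1.1 concern repeat laboratory tests and separate samples, and participants without EMD are scheduled for imaging only yearly or as clinically indicated.

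The cost is a revision of the affected text in both documents and a little extra programming. Under the first option, a few PDs may become unconfirmed and be censored.

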6.3.2. Complete Response Rate

CRR is defined as the proportion of participants with a BOR of confirmed sCR or CR per IMWG criteria as determined by investigator.

Point estimates of CRR will be calculated along with corresponding 2-sided exact 95% CIs using the Clopper-Pearson method.

6.3.3. Duration of Response

DOR is defined, for participants with an objective response per IMWG criteria as determined by investigator, as the time from the first documentation of objective response that is subsequently confirmed, until confirmed PD per IMWG criteria, or death due to any cause, whichever occurs first. The rules for PD confirmation are described in [Table 4](#).

DOR will be calculated as follows:

$$\text{DOR (months)} = [\text{date of event or censoring} - \text{first date of objective response} + 1] / 30.4375$$

The censoring rules for DOR are as described for PFS in [Section 6.3.5](#) except that participants will not be censored for no adequate post-baseline assessment, as only participants with an objective response are included in the analysis of DOR.

If at least 3 participants achieve an objective response and subsequently have an event, DOR will be estimated using the same Kaplan-Meier method as described for PFS in [Section 6.3.5](#) and displayed graphically where appropriate. Otherwise only listings will be provided.

The DOR rate at 3, 6, 9, and 12 months (and in subsequent 6-month increments while there are participants still at risk) will be estimated with corresponding two-sided 95% CIs.

For sensitivity analyses on DOR, if $\geq 10\%$ of responders have died due to COVID-19 related reasons, these participants will be censored at the time of death.

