#### **Duration of Response**

DOR is defined, for participants with an objective response per IMWG criteria, as the time from the first documentation of objective response that is subsequently confirmed, until confirmed PD per IMWG criteria, or death due to any cause, whichever occurs first.

DOR will be censored on the date of the last adequate disease assessment for participants who do not have an event (PD or death due to any cause), on the date of the last adequate disease assessment before the new anti-cancer therapy for participants who start a new anti-cancer therapy prior to an event, or on the date of the last adequate disease assessment before the 2 or more missing disease assessments for participants with an event after 2 or more missing disease assessments.

DOR will be summarized using Kaplan Meier method and displayed graphically. Median DOR and 2-sided 95% CI (based on the Brookmeyer-Crowley method) will be provided.

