### **Duration of Complete Response**

DOCR is defined, for participants with a BOR of confirmed sCR/CR per IMWG criteria, as the time from the first documentation of sCR/ CR that is subsequently confirmed, until confirmed PD per IMWG criteria, or death due to any cause, whichever occurs first.

DOCR will be censored on the date of the last adequate disease assessment for participants who do not have an event (PD or death due to any cause), on the date of the last adequate disease assessment before the new anti-cancer therapy for participants who start a new anti-cancer therapy prior to an event, or on the date of the last adequate disease assessment before the 2 or more missing disease assessments for participants with an event after 2 or more missing disease assessments.

DOCR will be summarized using Kaplan Meier method and displayed graphically. Median DOCR and 2 sided 95% CI will be provided.

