5.2. General Methods

Unless otherwise specified, all efficacy analyses and safety analyses will be performed using the Safety Analysis Set. All analyses will be performed by part as follows:

- Part 1;
- Part 2;
 - Part 2A Dose level 1 (if Dose level 2 is identified as RP2D);
 - Part 2A (RP2D) + Part 2B;
 - CCI
- Part 1 and Part 2 Combined.

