6. ANALYSES AND SUMMARIES

The primary analysis will be conducted once all enrolled participants have completed Cycle 1 or have otherwise discontinued the study intervention. At this analysis, the primary endpoint of Grade ≥ 2 CRS rate during Cycle 1 and the safety endpoints will be evaluated.

For primary completion date reporting purpose (initial CSR), the full scope of the statistical analysis including all the endpoints will be conducted once all participants have been followed for response for at least 6 months or have otherwise discontinued response assessments within the first 6 months of treatment.

The final analysis will be conducted once the last participant enrolled will have been followed for OS for at least 2 years.

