6.3.4. Duration of Complete Response

DOCR is defined, for participants with a BOR of confirmed sCR or CR per IMWG criteria as determined by investigator, as the time from the first documentation of sCR or CR that is subsequently confirmed, until confirmed PD per IMWG criteria, or death due to any cause, whichever occurs first. The rules for PD confirmation are described in [Table 4](#).

DOCR will be calculated as follows:

$$\text{DOCR (months)} = [\text{date of event or censoring} - \text{first date of sCR or CR} + 1] / 30.4375$$

The censoring rules for DOCR are as described for PFS in [Section 6.3.5](#).

If at least 3 participants achieve a BOR of confirmed sCR or CR and subsequently have an event, DOCR will be estimated using the same Kaplan-Meier method as described for PFS in [Section 6.3.5](#) and displayed graphically where appropriate. Otherwise only listings will be provided.

The DOCR rate at 3, 6, 9, and 12 months (and in subsequent 6-month increments while there are participants still at risk) will be estimated with corresponding two-sided 95% CIs.

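### SAP 6.3.3 and 6.3.4 withhold Kaplan-Meier estimates of DOR and DOCR until 3 responders have progressed or died, which ties reporting to the outcome and matters for Dose level 1 and for DOCR in the smaller groups

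*SAP*

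**What the plan says.** SAP 6.3.3 makes the DOR analysis conditional: "If at least 3 participants achieve an objective response and subsequently have an event, DOR will be estimated using the same Kaplan-Meier method". If the condition fails, "Otherwise only listings will be provided". SAP 6.3.4 repeats the rule for complete responders: "If at least 3 participants achieve a BOR of confirmed sCR or CR and subsequently have an event, DOCR will be estimated". Each section then promises landmark estimates with no condition; for DOR it begins "The DOR rate at 3, 6, 9, and 12 months".

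Protocol 9.3.3.2 has no event threshold. It states "DOR will be summarized using Kaplan Meier method and displayed graphically" and, for complete responders, "DOCR will be summarized using Kaplan Meier method and displayed graphically". SAP 6.3.5 (PFS) and 6.3.6 (OS) set no minimum number of events either.

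Two other sections determine where the rule has an effect. SAP 5.2 reports by group: Part 1, Part 2A Dose level 1 on its own when Dose level 2 is the RP2D, the RP2D group with Part 2B, and all combined. SAP 6 sets the full analysis for the initial CSR once all participants have been "followed for response for at least 6 months" or have stopped response assessments earlier, with a final analysis after at least 2 years of survival follow-up.

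**The concern.** The condition counts events, not responders. Ten responders who are all still in response produce no curve; three responders who all progress produce one. An estimate is therefore withheld when responses last, and in a small group any estimate that does appear has been selected for early progression.

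The rule also cannot be programmed as written. With 0 to 2 events, a listings-only output and an estimated 3-, 6-, 9- and 12-month rate cannot both be delivered.

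What is at stake is the description of durability by dosing regimen, which belongs to a stated secondary objective. No test or decision rule is involved.

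**Working it through.** The documents give no expected number of DOR or DOCR events and no chance of meeting the condition, so there is no plan figure to reproduce.

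**Inputs from the documents**
- Dose level 1: 12 treated (Protocol 4.1).
- Part 1: about 30 (Protocol 4.1).
- RP2D group: 11 treated at Dose level 2 plus about 22 in Part 2B, so 33.
- All combined: about 76.

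**Assumptions (the plan states none)**
- Duration is exponential with median M of 11.0 or 21.8 months. Both values stand in Protocol Table 3, for other therapies.
- Response rate is 60-72%; CR rate is 20-40%.
- Follow-up from response is uniform between a and b months.
- The condition is applied within each reporting group.

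**Chance of meeting the condition**

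With λ = ln 2 / M, the chance that a responder has an observed event is

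q = 1 − (e^(−λa) − e^(−λb)) / (λ(b − a)).

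Events in a group of n follow Binomial(n, rate × q).

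Example: Dose level 1, response rate 60%, M = 21.8, follow-up 5-11 months.
- λ = 0.0318
- q = 1 − (0.8530 − 0.7049)/0.1908 = 0.223
- Event probability per participant = 0.60 × 0.223 = 0.134; expected events = 12 × 0.134 = 1.6
- P(0) + P(1) + P(2) = 0.178 + 0.330 + 0.281 = 0.789, so P(at least 3) = 0.21

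**Effect on the reported rate**

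The true 6-month DOR rate at M = 21.8 is 2^(−6/21.8) = 0.83. The mean Kaplan-Meier estimate among groups that meet the condition comes from simulation (20,000 groups per setting). Without the condition the simulated mean was 0.83 in every DOR setting below.

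DOR, M = 21.8, response rate 60-72%:

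| Group | Follow-up from response (months) | P(at least 3 events) | Mean 6-month rate when reported |
|---|---|---|---|
| Dose level 1, n=12 | 5-11 | 0.21-0.30 | 0.66-0.70 |
| Dose level 1, n=12 | 10-17 | 0.47-0.61 | 0.75-0.78 |
| Part 1, n=30 | 5-11 | 0.79-0.88 | 0.80-0.81 |
| RP2D group, n=33 | 5-11 | 0.84-0.92 | 0.81-0.82 |
| Combined, n=76 | 5-11 | above 0.99 | 0.83 |

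At M = 11.0 with 5-11 months, P(at least 3) is 0.56-0.70 for Dose level 1 and 0.98-1.00 for n = 30 and n = 33.

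DOCR, M = 21.8, CR rate 20-40%, P(at least 3 events):

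| Group | 1-8 months from CR | 6-15 months from CR |
|---|---|---|
| n=12 | 0.00-0.02 | 0.03-0.14 |
| n=30 | 0.04-0.21 | 0.24-0.67 |
| n=33 | 0.055-0.25 | 0.28-0.73 |

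**Sensitivity**

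A separate simulation used follow-up of 6-18 months from first dose, with assumed times of 1.5 months to response and 4 months to CR.
- DOR, n = 30, response rate 60%: the condition failed in 1%, 4% and 9% of runs at medians of 11, 17 and 22 months.
- DOR, n = 30, response rate 30%: it failed in 17%, 39% and 53%.
- DOR, n = 30, response rate 60%, everyone followed for exactly 6 months: it failed in 15%, 40% and 59%.
- DOCR, CR rate 30%, medians of 17 and 22 months: it failed in 56% and 67% at n = 30, and in 4% and 13% at n = 76.

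**Final analysis**

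With 24-36 months of follow-up and medians of 17 and 22 months, the condition failed as follows.
- DOR, response rate 60%: 0% and 0% at n = 30; 6% and 15% at n = 12.
- DOCR, CR rate 30%: 5% and 10% at n = 30; 58% and 66% at n = 12.

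**The case against.** A reader might infer that most groups will miss the condition at the first full analysis, that durable results will go unreported, and that every reported DOR estimate is biased low. The documents do not support that.

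- Six months is a minimum, set by the last participants. Part 2 opens after about 30 have enrolled in Part 1, Dose level 2 only if Dose level 1 is tolerable, and Part 2B only after the RP2D is selected. Part 1 and Dose level 1 will therefore have been followed for longer, which is why the 10-17 month row is included.
- For DOR at response rates of 60% or more, groups of about 30 usually meet the condition, and the bias there is at most about 0.03.
- Individual durations are still listed, a later final analysis is planned, and PFS is estimated without any event condition.
- The study is non-randomised, has no formal testing, and specifies no comparison of DOR between regimens. Protocol section 9 allows the SAP to modify planned methods, so the added condition is not in itself a breach.

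All of this stands, and it limits the size of the problem. It does not remove the dependence on outcome or the conflict within each section. Nor does it help Dose level 1 when responses last, or DOCR in the separate groups. Sparse events are no reason to suppress the analysis: landmark rates can be estimated with few events, and SAP 5.3 already provides NR for a statistic that is not reached.

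**Conclusion.** The point holds with limited scope. The rule makes reporting of two secondary endpoints depend on the outcome, conflicts with the landmark sentence in the same section, and departs from Protocol 9.3.3.2 without a stated reason.

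The effect is material in two places:
- DOR in Part 2A Dose level 1 when responses are durable. The condition is met in about 21-61% of cases at a 21.8-month median, and the reported 6-month rate averages about 0.66-0.78 against 0.83.
- DOCR in groups of about 30 or fewer at the initial CSR.

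It is small for DOR in the groups of about 30 at response rates of 60% or more (condition met in about 79-100%). It is absent for DOR in the combined set. DOR in the 30-participant groups would be affected more if the response rate were near 30% or follow-up were barely 6 months for everyone. Most of the larger groups meet the condition by the final analysis.

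These sizes rest on assumed response rates, durations and follow-up, and on applying the condition within each group as SAP 5.2 implies. The conflict in the text needs no assumption.

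**What to change.** In SAP 6.3.3 and 6.3.4, delete the event condition or replace it with a minimum number of responders, for example at least 3 responders for DOR and at least 3 with sCR or CR for DOCR. For every group analysed, give the numbers of responders, events and participants at risk, the Kaplan-Meier curve, and the 3-, 6-, 9- and 12-month rates. Show the median as NR when it is not reached. This agrees with Protocol 9.3.3.2 and with the SAP's own NR convention.

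The cost is one sentence in each of two sections, with no new data. The downside is that intervals will be wide with 1 or 2 events and not estimable by the log(-log) method with none; they should be shown as such.
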